### **Mobile Application and EMA**

There are two versions of the mobile application, depending on the condition: EMA or EMA + Mindfulness. Participants will be randomized using a true randomization procedure (i.e., rolling die with even or odd number determining their condition). The first time they use the mobile application (i.e., during the lab visit), participants enter a unique identification number. Thus, all responses will be logged electronically based on the identification number. Participants are also prompted to enter their wake time and bed time. The application uses this information to time the three daily notifications. Adolescents will be told to respond as soon as possible after receiving a notification, but instructed not to use the phone if they were in a situation where it is not permitted. When accessing the application, adolescents will respond to 10 EMA questions assessing the following:

*Time and place.* Participants are asked whether they are thinking about the past, present, future; whether they are alone or with others and where they are located (e.g., school, home, other). These questions were adapted from a large EMA study (Killingsworth & Gilbert, 2010).

*State rumination.* Participants will respond to two questions regarding focus on emotions and focus on problems using a sliding scale from 0 to 100 for each. These questions were adapted from a previous EMA study on rumination (Moberly & Watkins, 2008) and have been used to assess state rumination in other work (e.g., Hilt & Pollak, 2012; Hilt, Sladek, Doane, & Stroud, 2017).

*State mood.* Using sliding scales ranging from 0 to 100, participants indicate how happy, sad, calm, and anxious they currently feel.

*State mindfulness.* Participants rate their degree of focusing on bodily sensation using a 0 to 100 scale.

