### **Mindfulness Intervention**

In the EMA + Mindfulness condition, participants have a 67% chance of receiving a mindfulness exercise, unless their sad or anxious mood rating is 90 or above, in which case their chance is 85%. This graded strategy was chosen so that participants would not be able to easily figure out the mood rating that results in an exercise and so that participants would have a greater chance of receiving an exercise when they most needed it.

If an exercise is assigned, participants are prompted to enter how much time they have to engage in an activity (from 0-15 minutes). There are three 1-minute exercises (written instructions for focusing on the breath, sounds, or physical sensations); six 3-5 minute exercises (guided audio focusing on breathing, sounds, or body scan); and five 10-12 minute exercises (guided audio focusing on breath, body scan, or mountain metaphor).

Participants who indicate having less than 5 minutes receive one of the 1-minute exercises, those who indicate having at least 5 minutes receive either a 1-minute or a 3-5 minute exercise, and those who indicate having at least 12 minutes receive any exercise. Exercises are randomly assigned based on these parameters. The guided audio exercises were chosen based on those freely available that represent the type of mindfulness exercises typically found in MBSR courses, appeared accessible for adolescents, featured a variety of voices, and performed well in pilot testing. Following each mindfulness exercise, participants were prompted with the same EMA questions plus an additional question asking how helpful the activity was, rated on a 0-100 sliding scale.

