The primary hypothesis can also be examined on a finer-grain time scale using state-level EMA data to test whether a mindfulness exercise results in reduced negative mood immediately or at subsequent time points relative to each person's average level of mood. Relatedly, we can examine whether mindfulness exercises reduce state rumination compared to one's average level of state rumination and if so, test mediation. Similar to the trait-level models, covariates (i.e., between-person factors such as sex, SES, and race/ethnicity) may be included if warranted. These multilevel models will be estimated in Mplus (Muthén & Muthén, 1998-2015) using maximum likelihood estimation with robust standard errors to account for the nested nature of the data. This approach will allow for the examination of between- and within-person variation in outcomes and is consistent with current recommendations for handling missing data (Baraldi & Enders, 2010).

Although rumination is the proposed mediator, we can also test an alternative mechanism, i.e., changes in mindfulness (**Exploratory Aim**). Another mindfulness intervention found that changes in state mindfulness predicted changes in trait mindfulness (Kiken, Garland, Bluth, Palsson, & Gaylord, 2015). Furthermore, there appears to be an inverse relationship between trait mindfulness and depressive symptoms (e.g., Way, Creswell, Eisenberger, & Liberman, 2010). Thus, it is possible that the intervention will improve symptoms by increasing mindfulness, reducing rumination, or both. Both trait- and state-level mindfulness can be included as mediators in the above-mentioned models (Preacher & Hayes, 2008).

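### The state-level EMA test does not account for the mood rule that sets each session's chance of an exercise, so next-prompt effects lean toward harm; the immediate effect has no control

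*Combined protocol and SAP*

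**What the plan says.** **Assignment.** Under Mindfulness Intervention, in the EMA + Mindfulness arm, "participants have a 67% chance of receiving a mindfulness exercise, unless their sad or anxious mood rating is 90 or above"; above that threshold the chance is 85%. One stated reason is that "participants would have a greater chance of receiving an exercise when they most needed it". The probability of an exercise therefore depends, by design, on the mood rated just before it.

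**Ratings.** Under Mobile Application and EMA, "When accessing the application, adolescents will respond to 10 EMA questions assessing the following", a list that includes sad and anxious mood and state rumination on 0 to 100 scales. A second set is described only in one case: "Following each mindfulness exercise, participants were prompted with the same EMA questions plus an additional question asking how helpful the activity was". No repeat rating is described for sessions without an exercise or for the EMA-only arm.

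**Analysis.** In the Statistical Analysis Plan, Specific Aim 2, the state-level models will "test whether a mindfulness exercise results in reduced negative mood immediately or at subsequent time points relative to each person's average level of mood" and will look at "whether mindfulness exercises reduce state rumination compared to one's average level of state rumination", followed by mediation. On adjustment it says that "covariates (i.e., between-person factors such as sex, SES, and race/ethnicity) may be included if warranted". The models are multilevel, fitted in Mplus with robust standard errors. The text does not mention the 67%/85% rule, the threshold of 90, the rating before the exercise, or a contrast of assigned with not-assigned sessions.

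**The concern.** The outcome at one prompt is related to mood at the previous prompt, and mood at the previous prompt helped to decide whether an exercise was given. Sex, SES and race/ethnicity do not change from session to session, so they cannot remove that imbalance. An exercise with no effect would then tend to be followed by worse mood than no exercise, and a helpful exercise would look weaker than it is.

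The immediate effect has a separate problem. With no second rating in sessions without an exercise, a change after the exercise cannot be told apart from re-rating, demand effects or regression to the mean.

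This is the plan's finer-grained test of the rumination mechanism. A masked benefit or a spurious signal of harm in distressed adolescents could mislead the decision on a larger trial.

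**Working it through.** The documents give no power, bias or variance figure for this analysis, so there is none to reproduce.

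**Inputs from the documents.** About 75 participants in the arm; 3 sessions a day for 21 days = 63 per person; 75 × 63 = 4,725 sessions at full use; exercise probability 0.67, or 0.85 at 90 or above.

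**Inputs assumed.** Autocorrelation between prompts 0.4, within-person SD 20, between-person SD 15, sad-anxious correlation 0.6, common mean 30, 45 or 55, ratings clipped to 0-100. These means put 1.5%, 6.2% and 13.2% of sessions at 90 or above when the exercise has no effect (below: about 1%, 6% and 13%).

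**Step 1: imbalance.** With h the share of sessions at 90 or above:

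- among exercise sessions, 0.85h / (0.85h + 0.67(1 − h));
- among no-exercise sessions, 0.15h / (0.15h + 0.33(1 − h)).

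| h | Exercise | No exercise | Difference |
|---|---|---|---|
| 1.5% | 0.01275/0.67270 = 1.90% | 0.00225/0.32730 = 0.69% | 1.21 points |
| 6.2% | 0.05270/0.68116 = 7.74% | 0.00930/0.31884 = 2.92% | 4.82 points |
| 13.2% | 0.11220/0.69376 = 16.17% | 0.01980/0.30624 = 6.47% | 9.71 points |

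**Step 2: bias at the next prompt.** Approximately, bias = difference in shares × mood gap between the two tiers × autocorrelation. The simulated null bias for the sad rating, using a person-centred exercise indicator without session covariates, was +0.17, +0.51 and +0.84 points (positive means harm). The formula returns these values for mood gaps of 0.17/(0.0121 × 0.4) = 35, 0.51/(0.0482 × 0.4) = 26 and 0.84/(0.0971 × 0.4) = 22 points, which are plausible on this scale. For rumination, with a correlation of 0.5 with mood, the bias was about +0.1, +0.3 and +0.5. With the tier in the model it was about 0.

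**Step 3: consequences.** The power row is for a 2-point reduction at the next prompt. Each cell runs over about 1%, 6% and 13% of sessions at 90 or above.

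| | Every prompt answered | 70% answered |
|---|---|---|
| False-positive rate, no session covariates (nominal 5%) | 7%, 13%, 29% | about 8-17% |
| Power, no session covariates | about 81%, 67%, 47% | about 54%, 37%, 25% |
| Power, tier and current rating | about 90% | 63-66% |

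**Step 4: sensitivity.** Over the same three shares, autocorrelation 0.2 gives a null bias of +0.1 to +0.4 and 0.6 gives +0.2 to +1.2. Within-person SD 15 gives 0.0 to +0.4 and SD 25 gives +0.4 to +1.4. A second simulation with other assumptions (70% answered, means 30/40/50, within-person SD 20/22/25, added rating noise, autocorrelation 0.2 or 0.5) gave +0.08 to +1.39 without the tier and −0.03 to +0.01 with it. Power there was 6-52% without the tier and 39-57% with it.

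**Step 5: comparator.** At full use the no-exercise sessions number 4,725 × (0.33 × 0.99 + 0.15 × 0.01) = 1,551 at h = 1%, and 4,725 × (0.33 × 0.87 + 0.15 × 0.13) = 1,449 at h = 13%.

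**Step 6: immediate rating.** In the second simulation, with no true immediate effect, the rating after an exercise compared with the person's own average came out at +0.13 to +0.90 points, with false harm in 7-86% of runs. A pre-to-post change has a different weakness: it has no counterpart without an exercise. Re-rating and demand effects cannot be sized from the documents.

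**The case against.** **The plan writes out no model.** A multilevel model of within-person variation could carry session-level terms, and the covariate sentence describes optional additions without ruling others out. That stands: this is an omission, not an exclusion. A reader might infer that the plan discards the app's session-level randomisation altogether. The documents do not support that, because an ordinary exercise indicator would use it, and the figures above come from such an indicator. But the indicator without the tier is what produces the bias.

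**The power loss depends on the reading.** Taken literally, as deviation from the person's own average, the reported effect shrinks to about one third at full use (mean 30: −0.54 against −1.62 points) with almost the same z (−2.98 against −2.93). At 70% answered the two readings part. Under the base assumptions the literal reading had power 55-73% against 25-54% for the indicator, because the own average then includes prompts that follow missed, exercise-free slots. In the second simulation it did worse (6-36% against 6-52%). So no single power loss can be attributed to the plan.

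**The threshold may rarely be reached.** This is a school-recruited prevention sample. At about 1% of sessions the bias is negligible. That stands, and the documents do not settle the share.

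**Prompts will be missed.** Reminders and a bonus show that full use cannot be assumed, so power near 90% after the fix is a ceiling.

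**The bias is conservative.** A reader might infer that the state-level test cannot produce a false benefit. That holds for the next-prompt analysis only; an uncontrolled pre-to-post change can.

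**Conclusion.** The point holds as an omission with a known direction. For the next-prompt analysis, the described comparison does not account for the mood that set the exercise probability. If mood carries over positively between prompts, the estimate leans toward harm and can hide a benefit. Under the base assumptions the null bias is about +0.2, +0.5 and +0.8 points, negligible at the low end; it rests on an assumed rating distribution and autocorrelation, and the power figures also on an assumed response rate. The absence of a control for the immediate effect follows from the documents and needs no assumption.

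Priority is minor to moderate. The state-level analysis is worded as something that can be done in addition, and the between-arm trait-level mediation models do not use session assignment. A reader might infer that the trial's main test of Aim 2 is compromised; nothing here supports that.

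**What to change.** State in the SAP:

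- **(a) Next-prompt analysis.** Within person, in the EMA + Mindfulness arm, contrast sessions assigned an exercise with sessions not assigned one, for mood and for rumination. The outcome is the first rating at the next app session, prompted or self-initiated, before any new exercise. Include the 90-or-above tier as a session-level covariate; this alone removes the bias. Add the current pre-exercise rating for precision (at full use, power of 87-89% with the tier alone against 92-93% with both, in one set of runs).
- **(b) Exposure.** Define exercise by assignment, not completion, if the app database records it.
- **(c) Immediate change.** Report the pre-to-post change as an uncontrolled description.

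The cost is SAP wording and one check of what the database records. Both covariates come from ratings already collected in each session. The downside is that the immediate change can no longer be presented as an effect of the exercise.

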Mindfulness interventions that show decreases in trait rumination typically involve instruction and home practice over the course of several weeks. For example, an 8-week Mindfulness Based Stress Reduction (MBSR; Kabat-Zinn, 1982) course that involves meeting for two hours once per week along with daily home practice resulted in decreased trait rumination in multiple studies with adult participants (e.g., Deyo, Wilson, Ong, & Koopman, 2009; Shapiro, Brown, & Biegel, 2007). Similarly, a month-long mindfulness intervention with distressed college students showed decreases in trait rumination that were not seen in the active control condition (Jain et al., 2007). Although promising, these intensive interventions have not been examined for their effects on rumination with

adolescents. Furthermore, it is unclear how much practice is required to produce reductions in trait rumination.

Recent work by the PI has shown that a brief mindfulness intervention can reduce state (i.e., momentary) rumination. In two laboratory studies, one with college students (Villa & Hilt, 2014) and one with younger adolescents (Hilt & Pollak, 2012), the PI and her colleagues showed that an 8-minute guided mindfulness exercise reduced state rumination relative to active control conditions. These studies highlight the benefit of even brief mindfulness interventions for adolescents, but they do not show whether occasional or regular use of brief mindfulness exercises would impact trait rumination and subsequent psychopathology.

Because state rumination is positively associated with trait rumination (Moberly & Watkins, 2008), we expect that regular use of brief mindfulness exercises will allow adolescents to repeatedly make state adjustments that will reinforce a behavioral cycle leading to reductions in trait rumination and psychopathology.

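### The state-level exercise effect is planned as one average that ignores the rating given just before each random draw; if the effect grows with starting level, that average understates it at high levels

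*Combined protocol and SAP*

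**What the plan says.** Under Mindfulness Intervention, at each use of the app in the EMA + Mindfulness arm, "participants have a 67% chance of receiving a mindfulness exercise, unless their sad or anxious mood rating is 90 or above"; at or above that level the chance is 85%. Two reasons are given. Participants should not easily work out which rating triggers an exercise, and "participants would have a greater chance of receiving an exercise when they most needed it". State rumination does not enter the rule.

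Under Mobile Application and EMA, the ratings come before the draw: "Using sliding scales ranging from 0 to 100, participants indicate how happy, sad, calm, and anxious they currently feel". The two state rumination items use the same 0 to 100 range. The questions are repeated straight away only when an exercise has been given.

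Under Specific Aim 2 of the Statistical Analysis Plan, the multilevel models ask whether an exercise lowers negative mood, at once or later, relative to the person's average. For the proposed mechanism, "we can examine whether mindfulness exercises reduce state rumination compared to" the person's average, with mediation tested only if it does. The covariates named for these models are between-person factors (sex, SES, race/ethnicity) and are optional. The pre-draw rating is not mentioned. Moderators such as sex are discussed for the trait-level models only.

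**The concern.** An exercise is drawn about two times in three even when sadness, anxiety or rumination is rated close to 0, where a 0 to 100 scale leaves little room for a fall. If the benefit depends on where the person starts, one average mixes moments with little to gain and moments with much to gain. A small average could then be read as showing that exercises do little. Because state-level mediation is tested only after a reduction in state rumination is found, it could also end the state-level test of mechanism.

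The delivery rule also rests on an idea about need that no planned analysis examines. Yet the app records the rating, then draws at random with a known probability, so the data to examine it will exist.

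**Working it through.** The plan gives no state-level effect size, power or distribution of momentary ratings, so there is no figure of its own to reproduce.

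**1. Inputs.** From the documents: draw probabilities 0.67 and 0.85; threshold 90 on sad or anxious; 0 to 100 scales; about 75 participants in the arm; 3 prompts a day for 21 days, that is 63 per person. Assumed: the distribution of starting ratings, the shape of the effect, and the level called high.

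**2. Where the exercises fall.** At full compliance there are 75 × 63 = 4,725 prompts and at least 0.67 × 4,725 ≈ 3,166 exercises. The rule favours high distress by 0.85/0.67 = 1.27. If a share p of prompts is at 90 or above, their share of exercises is s = 0.85p / (0.85p + 0.67(1 − p)). For p = 5%, s = 0.0425/0.679 = 6.3%; for p = 10%, s = 12.3%. Unless high ratings are common, most exercises fall at ordinary or low ratings.

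**3. Effect at high levels divided by the average effect.**

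| Assumed effect shape | Assumed ratings | Ratio |
|---|---|---|
| Constant | any | 1.0 |
| Half constant, half proportional | Beta, mean 15 to 50; high = 50, 70 or 90 and above | 1.1 to 1.7 |
| Proportional, read at 70 | mean 14, 22, 31 | 70/14 = 5.0; 70/22 = 3.2; 70/31 = 2.3 |
| Proportional, high = 90 and above | Beta, mean 15 to 50 | 6.0 down to 1.9 |
| All-or-none at 90 and above (ratio 1/s) | p = 5%, 10%, 20%, 40% | 16.0, 8.1, 4.2, 2.2 |

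In the proportional rows the ratio is little more than the reading level divided by the assumed mean. It measures the assumption, not the trial.

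**4. Power, by simulation.** Common settings: 75 participants, 47 sessions each, within-person SD about 20, ratings clipped at 0 and 100, the draw probabilities above, person-clustered standard errors. Ranges cover several sets of runs with different secondary settings (one used a between-person SD of 12 and a carry-over of 0.3).

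| Assumed effect | Mean rating | Power, average effect | Power, effect at 70 |
|---|---|---|---|
| 5% of starting rating | about 14 | 13–22% | 21–33% |
| 5% of starting rating | about 22 | 29–40% | 42–55% |
| 5% of starting rating | about 31 | 54–63% | 61–80% |
| Constant 2 points | about 14 to 31 | 67–81% | 15–34% |

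The advantage of reading at 70 exists only when the effect scales with the starting level, and it reverses when the effect is constant. In one set of runs 0.4%, 1.6% and 4.4% of sessions started at 70 or above. Of 75 × 47 = 3,525 sessions that is about 14, 56 and 155, so an estimate at 70 would be largely linear extrapolation.

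Adjusting the average effect for the pre-draw rating reduced its standard error by 2 to 4% in every setting tried.

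**5. Which comparison is randomised.** The draw is random given the 67%/85% stratum, which depends on sad and anxious together. At p = 5%, prompts at 90 or above make up 6.3% of exercise draws but 0.15 × 0.05 / (0.15 × 0.05 + 0.33 × 0.95) = 0.0075/0.321 = 2.3% of no-exercise draws. Adjusting only for the outcome's own pre-draw rating leaves that imbalance in a rumination model, because rumination is not in the rule, and in a sadness model, because anxiety is. The immediate second rating exists only after an exercise. A fall from a high start on that rating is partly regression to the mean, with no no-exercise moments to set against it. The next prompt's rating is requested after both kinds of draw.

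**The case against.** The strongest case against is that the average is the right target. The Background describes the mechanism as frequent practice: "regular use of brief mindfulness exercises will allow adolescents to repeatedly make state adjustments". The preference for distressed moments is only 1.27-fold, it ignores rumination, and it shares its rationale with concealing the trigger. The average under the app's own delivery rule therefore answers a question the trial asks. This stands, and it is why the average should remain the main state-level estimate.

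A reader might infer that the planned effect is diluted two- to five-fold. The documents do not support that. They give no rating distribution and no effect shape, and the factor follows from assuming a proportional effect, means of 14 to 31 and a reading at 70. The Sample section requires at least moderate trait rumination, which does not settle what momentary ratings will look like. A reader might also infer that the effect at a high level is the better-powered test; step 4 shows that this depends on the assumed shape.

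It is also fair that the plan's wording is permissive, so a starting-level moderator is not ruled out, and that these models supplement the trait-level comparison of conditions, which is unaffected. But an interaction chosen after the data are seen is weak evidence, and none is specified now.

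**Conclusion.** The point holds as a minor improvement. The state-level models as written give one average effect and leave the pre-draw rating unused, although it is already collected and precedes the draw. If the effect rises with starting level, the average understates it at high levels; if the effect is constant, nothing is lost. The ratio cannot be fixed from the documents and runs from 1.0 to about 16 over the assumptions tabulated.

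Two stronger conclusions do not follow. The average is not invalid. Nor would every analysis by starting level be a randomised comparison: that requires adjustment for the draw stratum and an outcome requested after both kinds of draw.

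**What to change.** In the state-level section of Specific Aim 2, specify for the intervention arm:

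- Compare exercise with no-exercise draws on the next prompt's rating, for negative mood and for state rumination. Adjust for the pre-draw rating of the same outcome and for an indicator of the draw stratum (sad or anxious at 90 or above).
- Keep the average effect from this model as the main state-level estimate.
- Add one pre-specified interaction of the draw with the pre-draw rating. Report the effect at stated starting levels that the observed ratings support, beside the average. Base any statement about moments of greatest need on this interaction.
- Do not fit the interaction to the immediate post-exercise rating.

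The cost is a few model terms on data already collected, and one more test under the plan's general commitment to correct for multiple testing. If the effect is in fact constant, the estimates at high levels will be less precise than the average, and the report should say so.
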